7.8.2 Laboratory Tests

The following laboratory tests will be performed at Visit 1 Screening and Visit 5 Day 14.

Serum Chemistry	ALT	AST	BUN
	Total Bilirubin	Glucose	Creatinine
Hematology	Hemoglobin	Total WBC count with differentials	
Urinalysis	Appearance	Specific Gravity	Protein
	pH	Microscopic examination	

If warranted, other tests or examinations may be performed at the discretion of the investigator.

Actual values and changes from baseline for laboratory test results will be summarized descriptively by visit and treatment group. Test results will be presented in conventional units.

Additionally, numeric Serum Chemistry, Hematology and Urinalysis results will be classified as Low (below the reference range), Normal (within the reference range) or High (above the reference range). Categorical Urinalysis results will be classified as Normal or Abnormal. Shifts among these categories between baseline and Visit 5 Day 14 will be provided.

All results will be listed.

7.8.3 Vital Signs

Vital signs, including systolic and diastolic blood pressure, pulse rate, respiratory rate and body temperature will be assessed at all study visits. Overall interpretation will be recorded as Normal, Abnormal Not Clinically Significant or Abnormal Clinically Significant.

Height and weight will be measured and BMI will be calculated at Visit 1 Screening and Visit 5 Day 14+/-2.

Actual values and changes from baseline for vital signs (including height, weight and BMI) will be summarized descriptively by visit and treatment group. Overall interpretation will be summarized categorically by visit and treatment group. All vital signs results (including height, weight and BMI) will be listed.

7.8.4 Physical Examination

Physical examination will be performed at Visit 1 Screening and Visit 5 Day 14+/-2. The following body systems will be examined: General Appearance, Skin, HEENT, Heart, Lungs, Musculoskeletal System, Lymph Nodes, Neurological Systems, Gastrointestinal System, Genitourinary System, Extremities and Other if necessary. Each body system will be classified as Normal, Abnormal Not Clinically Significant or Abnormal Clinically Significant.

Number and percentage of subjects with each assessment result will be tabulated by body system, visit and treatment group. All results will be listed.

7.8.5 Visual Acuity

Subjects' visual acuity will be measured during Visit 1 Screening, Visit 4 Day 7 +/-2 and Visit 5 Day 14+/-2. Visual acuity will be tested using the subjects best-available spectacle correction with a Snellen chart. Best Corrected Visual Acuity will be recorded in Snellen units.

Snellen denominator and its change from baseline will be summarized descriptively by eye (study or non-study) visit and treatment group.

All results will be listed.

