#### 4.2 Inclusion Criteria

1. Males or non-pregnant, non-lactating females, 18 years of age or older who have a cataract and are expected to undergo cataract extraction.

2. No aqueous cells, no visible aqueous flare and no significant ocular pain in the selected eye noted during the Screening visit by slit-lamp examination.

No aqueous cells	Grade 0
No visible aqueous flare	Grade 0
No significant ocular pain	Grade 0 or 1
For details See Table 1 on page 13	

- 3. Study subjects must have provided IRB approved written informed consent using the latest version of the IRB informed consent form. In addition, study subjects must sign a HIPAA authorization, if applicable.
- 4. Study subjects should be literate and willing to complete the subject diary regularly as directed.
- 5. Study subjects must be in good health and free from any clinically significant disease apart from indication under study.
- 6. Females of child bearing potential (WOCBP\*) must not be pregnant or lactating at baseline visit (as documented by a negative urine pregnancy test).
  \*All female subjects will be considered to be of childbearing potential unless they are postmenopausal. Female subjects of childbearing potential (WOCBP) are defined as sexually mature women without prior hysterectomy, or who have had any evidence of menses in the past 12 months. However, women who have been amenorrheic for the past 12 or more months are still considered to be of childbearing potential, if the amenorrhea is possibly due to other causes, including prior chemotherapy, antiestrogens, or ovarian suppression. Postmenopausal women (defined as women who have been amenorrheic for at least 12 consecutive months, in the appropriate age group, without other known or suspected primary cause) or women who have been sterilized surgically or who are otherwise proven sterile (i.e., total hysterectomy, or bilateral oophorectomy with surgery at least 4 weeks prior to randomization) are not considered WOCBP. Subjects who have undergone tubal ligation are NOT considered as surgically sterile.

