#### 43 Exclusion Criteria

- 1. Females who are pregnant, breast feeding, or planning a pregnancy during the course of the study and for 30 days after last study dose.
- 2. Females of childbearing potential who do not agree to utilize an adequate form of contraception.
- 3. Current or past history of severe hepatic or renal impairment, uncontrolled diabetes mellitus, rheumatoid arthritis or bleeding tendencies.
- 4. Current or history within two months prior to baseline of clinically significant ocular disease, e.g., corneal denervation, corneal epithelial defects, severe dry eye syndrome, ocular trauma to the operative eye, corneal edema, proliferative diabetic retinopathy in the operative eye or ocular infection.
- 5. In the operative eye, history of chronic or recurrent inflammatory disease, e.g., iritis, scleritis, uveitis, iridocyclitis or rubeosis iritis, lens pseudoexfoliation syndrome with glaucoma or zonular compromise.
- 6. Congenital ocular anomaly, e.g., aniridia or congenital cataract in the operative eye.
- 7. Iris atrophy in the operative eye in the operative eye.
- 8. Current corneal abnormalities that would prevent accurate IOP readings with the Goldmann applanation tonometer in the operative eye.
- 9. Nonfunctional nonoperative eye (visual acuity of 20/200 or worse Snellen).
- 10. Known hypersensitivity to any component of nepafenac therapy or to other nonsteroidal anti-inflammatory drug (NSAID).
- 11. Use within one week prior to baseline in either eye of: Topical, ophthalmic, e.g. cyclosporine (Restasis®), or systemic NSAID.

- 12. Use within one month prior to baseline in either eye of: 1) systemic corticosteroid, 2) high-dose salicylate therapy, or 3) topical ophthalmic prostaglandin analogs, e.g., bimatoprost, latanoprost, or travoprost.
- 13. Use of systemic analgesic medications, e.g. narcotics, tramadol, Neurontin® within 48 hours of baseline. Exceptions are salicylate therapy 81mg or less per day, and acetaminophen not within 8 hours of any visit from Visit 1 until V5.
- 14. Use within six months prior to baseline of intravitreal or subtenon injection of ophthalmic corticosteroid in either eye.
- 15. Underwent within six months prior to baseline any complicated intraocular surgery or repeat ocular surgeries (e.g., cataract surgery) in the operative eye.
- 16. Underwent within twelve months prior to baseline: refractive surgery, filtering surgery or laser surgery for IOP reduction in the operative eye.

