# Ophthalmic Evaluation (To be performed on both the operative and non-operative eye.)

Following examinations will be performed during study visits:

**Best Corrected Visual Acuity**: Subjects visual acuity will be measured during Visit 1, 4 & 5. Visual acuity will be tested using the subjects best-available spectacle correction with a Snellen chart. Best Corrected Visual Acuity will be recorded in Snellen units. Pinhole correction is acceptable method of correction to use for post-surgical visit measurements.

**Assessment of Ocular Pain:** When using the scale, the investigator should describe the meaning of pain to the subject. Then, verbally the subject should be asked to choose one of the six descriptors (provided in table no. 1 on page no. 13) that best represent the level of pain intensity a subject is experiencing.

**Slit Lamp Examination:** Complete slit-lamp evaluation including evaluation of the anterior eye segment for presence of aqueous cells and flare, lids, cornea, Anterior Chamber, iris and conjunctiva. Anterior Chamber evaluation is to be administered using a narrow slit beam (0.5 width at least 8 mm length) at maximum luminance. Pigment and red blood cells are to be ignored.

**Intraocular Pressure Measurement by Goldmann Applanation Tonometry:** Measurement of intraocular pressure will be recorded in millimeters of mercury (mmHg) by using Goldman applanation tonometry (manual version) during all visits except Visit 2 (On the day of cataract surgery).

**Dilated Fundus Examination:** A dilated fundus examination will be administered on the day of screening and at the end of the study visit (Visit 5 or early exit). In it, appropriate eye drops will be used to dilate or enlarge the pupil in order to obtain better view of the fundus of the eye. Once the pupil is dilated, an ophthalmoscope or indirect lens will be used to view the eye structures:

Lens	For opacities and other challenges	
Vitreous	Normal or Abnormal. Any changes, character	or location
CONFIDENTIAL Page 22 of 63		Page 22 of 63

Retina	Any pathological finding
Optic Nerve Head	Normal/ glaucomatous, horizontal and vertical cup/disc ratio

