4. STUDY ENDPOINTS/OUTCOMES

Primary Efficacy Endpoint

The primary efficacy endpoint is the proportion of subjects with cure at Day 14 defined as a score of 0 for aqueous cells, a score of 0 for aqueous flare and a score of no more than 3 for pain.

Safety Endpoints

The safety endpoints include:

- The incidence of treatment emergent adverse events.
- Ocular parameters (visual acuity, intraocular pressure measurement, slit lamp evaluation and dilated fundus examination).

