7. STATISTICAL METHODS OF ANALYSIS

7.1 General Principles

The statistical analyses will be performed by [REDACTED] under the direction of the Sponsor, Actavis LLC, using SAS Version 9.4 (or higher). All tables, figures, and listings will be produced in the landscape format.

In general, all data will be listed by treatment group, subject and visit/time point where appropriate. The summary tables will also be stratified by, or have columns corresponding to, treatment groups.

All subjects will be identified by their unique subject numbers.

The total number of subjects in the study group (N) under the stated population will be displayed in the header of summary tables.

Data will be summarized using descriptive statistics for continuous variables. Unless otherwise specified, descriptive statistics will include number of subjects, mean, standard deviation, minimum, median, and maximum. The minimum and maximum statistics will be presented to the same number of decimal places as the original data. The mean and median will be presented to one more decimal place than the original data. The standard deviation will be presented to two more decimal places than the original data. The number of missing observations will be presented only if non-zero.

In summary tables of categorical variables, counts, and percentages will be used. The count [n] indicates the actual number of subjects in a particular category, which should always be less than or equal to the total number of subjects in the respective study group with known (non-missing) category [M]. Percentage will be obtained by: $\% = n/M * 100$. Unless otherwise stated, all percentages will be expressed to one decimal place.

All statistical tests will be two-sided at a significance level of $\alpha = 0.05$, unless otherwise indicated. No adjustment will be made for multiplicity.

The eye on which the cataract surgery is performed will be referred to as the study eye, and the other eye as the non-study eye. Ocular safety information will be presented separately for the study eye and non-study eye. Efficacy will be assessed for the study eye only.

Baseline will be defined as the last assessment obtained prior to the first dose of the study drug, unless otherwise specified.

Relative days will be calculated relative to date of first dose of study medication. Relative days will be calculated as follows only when the full assessment date is known (i.e., partial dates will have missing relative days).

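### Visual acuity, a safety endpoint, is summarised on the raw Snellen denominator, so a few very poor study eyes can dominate the mean and SD of change

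*SAP*

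**What the plan says.** Visual acuity is one of the ocular safety parameters named in SAP section 4 and in Protocol 7.0. Protocol 5.1 (Ophthalmic Evaluation) states that "Best Corrected Visual Acuity will be recorded in Snellen units". SAP 7.8.5 then plans that the "Snellen denominator and its change from baseline will be summarized descriptively by eye (study or non-study) visit and treatment group", and lists all results. It names no particular statistics, so the SAP 7.1 default applies: "descriptive statistics will include number of subjects, mean, standard deviation, minimum, median, and maximum".

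On entry, Protocol 4.2 item 1 admits patients "who have a cataract and are expected to undergo cataract extraction" and sets no acuity limit for that eye. The only acuity limit, Protocol 4.3 item 9, concerns the other eye: "Nonfunctional nonoperative eye (visual acuity of 20/200 or worse Snellen" is excluded.

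Neither document plans a logMAR or decimal conversion, a count of lines lost, or a rule for eyes that cannot read the chart.

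**The concern.** Equal differences in the denominator are not equal differences in acuity. A doubling is always 0.301 logMAR, but it is +20 from 20/20 and +200 from 20/200. An arithmetic mean of denominator changes therefore gives a very poor eye many times the weight of a typical one.

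Very poor study eyes can enter, and large gains after cataract removal are expected. The mean and SD of change can then reflect how many very poor eyes an arm happened to receive rather than how much acuity changed, and two arms can appear in the wrong order. What is at stake is the readability of a descriptive safety table.

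**Working it through.** The plan gives no acuity figure to reproduce. The documents give no acuity distribution and the allocation ratio is redacted, so every acuity below and 150 eyes per arm (450/3) are assumptions. Throughout, logMAR = log10(denominator/20).

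**1. Weight of one eye.** An eye going from 20/400 to 20/25 changes by 25 - 400 = -375. An eye worsening from 20/25 to 20/50 changes by +25. In a mean, the first cancels 375/25 = 15 of the second. On logMAR it cancels log10(400/25)/log10(50/25) = 1.204/0.301 = 4.

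**2. Constructed two-arm case, study eye.**
- Arm A: all 150 eyes go from 20/50 to 20/25.
- Arm B: all 150 eyes finish one line worse, at 20/32. Of these, 146 start at 20/50 and 4 (2.7%) at 20/400.

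| Summary | Arm A | Arm B | Order |
|---|---|---|---|
| Mean denominator change | 25 - 50 = -25.0 | [146(-18) + 4(-368)]/150 = -4100/150 = -27.3 (SD 56.6) | wrong |
| Mean logMAR change | log10(25/50) = -0.301 | [146 log10(32/50) + 4 log10(32/400)]/150 = -32.685/150 = -0.218 | right |
| Median denominator change | -25 | -18 | right |
| Visit 5 mean and median | 25 | 32 | right |
| Baseline maximum | 50 | 400 | exposes the imbalance |

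The four eyes supply 1472/4100 = 35.9% of arm B's total change on the raw scale and 4.388/32.685 = 13.4% on logMAR.

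**3. How often chance would do this.** Keep the same final acuities and let both arms contain poor eyes starting at 20/P, kA and kB in number. The raw mean changes are A = -25 - (P - 50)kA/150 and B = -18 - (P - 50)kB/150. The order reverses when kB - kA > 1050/(P - 50). On logMAR it reverses when kB - kA > 150 log10(32/25)/log10(P/50). Take kA and kB as independent Binomial(150, m/150), where m is the expected number of poor eyes per arm.

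| Poor-eye baseline | Excess needed, raw | Excess needed, logMAR | Raw reversal chance, m = 1 | m = 4 | m = 15 |
|---|---|---|---|---|---|
| 20/400 | 4 | 18 | 0.8% | 10.2% | 25.0% |
| 20/200 | 8 | 27 | <0.001% | 0.4% | 7.4% |
| 20/100 | 22 | 54 | ≤0.002% | ≤0.002% | ≤0.002% |

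The logMAR reversal chance is at most 0.04% in every cell. If exactly four such eyes exist across the two arms, all four fall in arm B with probability C(150,4)/C(300,4) = 6.1%.

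**4. A single arm with some spread.** Let 150 typical eyes start between 20/30 and 20/70 and finish between 20/20 and 20/30, then replace 3 (2%) with eyes going from 20/400 to 20/25.
- Raw change: the mean moves from -26.0 to -32.9 and the SD from 10.7 to 50.2. The three eyes carry 94% of the sum of squares.
- logMAR change: the mean moves from -0.305 to -0.323 and the SD from 0.073 to 0.145. The three eyes carry 74%.
- The median does not move on either scale.

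**The case against.** The plan contains no contradiction: acuity is recorded in Snellen units and summarised in those units, no test or decision rule uses the mean, and neither document promises logMAR. The same table carries the median, minimum, maximum and by-visit values, and everything is listed. A reader is misled only by taking the mean change alone and ignoring an SD of 56.6 beside it. This stands, and it is why the point is minor.

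The example is also built to reverse. If the four poor eyes finished at 20/200 rather than 20/32, arm B's mean would be [146(-18) + 4(-200)]/150 = -22.9, the right order. The larger reversal chances need 2.7% or 10% of eyes at 20/400, which nothing in the documents supports, and they presuppose a true one-line difference. This stands too: the example shows what can happen and does not forecast it.

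A further objection is that logMAR does not rescue the study eye as a safety measure, because surgical gain swamps any drug-related loss on either scale, while in the non-study eye the 20/200 exclusion largely removes extreme baselines. That is right, and it limits what the change buys. It does not justify keeping a mean and SD on a scale where they can mis-order the arms.

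Finally, an eye that cannot read the chart has no denominator to convert. That gap exists equally under the current plan.

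**Conclusion.** The concern holds, as a low-cost improvement worth considering. The non-linearity and the absence of an acuity limit for the study eye follow directly from the documents. The size rests on assumed acuities and 150 eyes per arm: the chance of mis-ordering two arms that truly differ by one line runs from negligible (poor eyes at 20/100) to about 25% (10% of eyes at 20/400), against at most 0.04% on logMAR. Only the mean and SD of change mislead; the other planned figures give the right order or reveal the imbalance. The effect is confined to descriptive safety reporting, and the equivalence and superiority conclusions do not depend on it.

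**What to change.** In SAP 7.8.5, derive logMAR = log10(denominator/20), and summarise logMAR and its change from baseline by eye, visit and arm in place of the denominator and its change. Keep raw Snellen values in the listing. State how an eye that cannot read the chart is handled, since neither scale has a value for it. This reduces the leverage of poor eyes but does not remove it.

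Optionally, add the number and percentage of eyes losing at least 0.3 logMAR (denominator at least doubled). That count is most informative in the non-study eye from baseline, and in the study eye from Visit 4 to Visit 5, where the pre-operative baseline no longer enters.

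The cost is one derived variable in one table and a unit less familiar to some readers. No new data are needed.

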7.8.6 Slit Lamp Examination

Complete slit-lamp evaluation including evaluation of eyelids, conjunctiva, sclera, cornea and iris will be performed at Visit 1 Screening, Visit 3 Day 1, Visit 4 Day 7+/-2 and Visit 5 Day 14+/-2. Each eye area examined will be classified as Normal, Abnormal Not Clinically Significant or Abnormal Clinically Significant.

Number and percentage of subjects with each assessment result will be tabulated by eye (study or non-study), eye area, visit and treatment group. All results will be listed.

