#### 5.3 Corneal Effects

Use of topical NSAIDs may result in keratitis. In some susceptible patients, continued use of topical NSAIDs may result in epithelial breakdown, corneal thinning, corneal erosion, corneal ulceration or corneal perforation. These events may be sight threatening. Patients with evidence of corneal epithelial breakdown should immediately discontinue use of topical NSAIDs including ILEVROTM (nepafenac ophthalmic suspension), 0.3% and should be closely monitored for corneal health.

Postmarketing experience with topical NSAIDs suggests that patients with complicated ocular surgeries, corneal denervation, corneal epithelial defects, diabetes mellitus, ocular surface diseases (e.g., dry eye syndrome), rheumatoid arthritis, or repeat ocular surgeries within a short period of time may be at increased risk for corneal adverse events which may become sight threatening. Topical NSAIDs should be used with caution in these patients.

Postmarketing experience with topical NSAIDs also suggests that use more than 1 day prior to surgery or use beyond 14 days post-surgery may increase patient risk and severity of corneal adverse events.

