3. STUDY OVERVIEW

3.1 Study Design

Approximately 450 subjects [REDACTED] will be enrolled and randomized in this investigational study. [REDACTED]

One drop of the suspension should be instilled into the affected eye one-time daily, beginning a day prior to the planned cataract surgery, on the day of the cataract surgery, and for 14 days thereafter. On the day of cataract surgery (day 0) a drop should be added 30-120 minutes prior to the surgery and an additional drop will be administered following cataract surgery prior to the subject leaving the surgery center. The study is designed to be only monocular (only one eye per subject).

The dose and mode of treatment chosen in this study is the dosage approved by US FDA for the treatment of pain and inflammation associated with cataract surgery.

The study subjects will undergo clinical evaluations throughout the study in order to assess efficacy and safety at the following visits:

- Visit 1: Day -21 to Day -1 (Screening/Baseline/Randomization Visit)
- Visit 2: Day 0 (The Day of Cataract Surgery)
- Visit 3: Day 1 (One Day After the Cataract Surgery)
- Visit 4: Day 7± 2 Days (Follow up Visit)
- Visit 5: Day 14 ±2 Days (End of Study Visit/Early Discontinuation)

An Unscheduled Visit is allowed at any time, for any reason, if in the Investigator's opinion it is warranted.

If the Investigator determines that the study subject's condition has worsened to the degree that it is unsafe for continuation in the study, the study subject may be discontinued and will be evaluated as a treatment failure.

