7.8.8 Dilated Fundus Examination

A dilated fundus examination will be administered at Visit 1 Screening and Visit 5 Day 14+/-2. In it, appropriate eye drops will be used to dilate or enlarge the pupil in order to obtain better view of the fundus of the eye. Once the pupil is dilated, an ophthalmoscope or indirect lens will be used to view the eye structures:

1. Optic Nerve Head: classified as Normal or Glaucomatous; horizontal and vertical cup/disc ratio measured.
2. Lens: examined for opacities and other challenges; classified as Normal, Abnormal Not Clinically Significant or Abnormal Clinically Significant
3. Vitreous: classified as Normal, Abnormal Not Clinically Significant or Abnormal Clinically Significant
4. Retina: classified as Normal, Abnormal Not Clinically Significant or Abnormal Clinically Significant

Number and percentage of subjects with each kind of assessment will be tabulated by eye (study or non-study), fundus structure, visit and treatment group. Horizontal and vertical cup/disc ratios will be summarized descriptively by eye (study or non-study), visit and treatment group.

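### SAP 7.8.6 and 7.8.8 count slit-lamp and fundus findings by visit only, so no aggregated examination table shows how many eyes per arm newly developed or worsened an abnormality

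*SAP*

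**What the plan says.** SAP section 4 lists as safety endpoints "Ocular parameters (visual acuity, intraocular pressure measurement, slit lamp evaluation and dilated fundus examination".

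Slit lamp (SAP 7.8.6): examined at Visits 1, 3, 4 and 5. "Each eye area examined will be classified as Normal, Abnormal Not Clinically Significant or Abnormal Clinically Significant". The planned summary is: "Number and percentage of subjects with each assessment result will be tabulated by eye (study or non-study), eye area, visit and treatment group". Results are also listed by subject.

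Fundus (SAP 7.8.8): examined at Visits 1 and 5. Lens, vitreous and retina use the same three grades; the optic nerve head is graded as normal or glaucomatous. The planned summary is: "Number and percentage of subjects with each kind of assessment will be tabulated by eye (study or non-study), fundus structure, visit and treatment group".

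Elsewhere the SAP links safety data to baseline. For categorised laboratory results (7.8.2): "Shifts among these categories between baseline and Visit 5 Day 14 will be provided". Vital signs (7.8.3), visual acuity (7.8.5) and intraocular pressure (7.8.7) are summarised with change from baseline. Physical examination (7.8.4) is not; it uses the same by-visit layout as the slit lamp.

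On visits outside the schedule (SAP 3.1): "An Unscheduled Visit is allowed at any time, for any reason". Sections 7.8.6 and 7.8.8 name only scheduled visits.

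**The concern.** A by-visit count is a net figure: abnormal at baseline, minus cleared, plus new. It cannot say how many eyes that were normal before surgery became abnormal, or how many moved up a grade. Nor can counts at separate visits be combined into the number of eyes that were abnormal at any time after surgery.

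Of the four named ocular endpoints, these two are the only ones not linked to baseline. The slit lamp is the planned examination of the cornea, and the label in Protocol Appendix III warns, under corneal effects, that "Use of topical NSAIDs may result in keratitis". If a product caused more new corneal findings, the examination tables would show the excess mixed with findings that were there before treatment. What is at stake is how visible a local safety difference is, not the efficacy conclusions.

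**Working it through.** The plan states no figure to reproduce here: it gives no expected rate for these findings, and the allocation ratio is redacted. The check is therefore an illustration on assumed rates.

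**Inputs**
- Total of about 450 subjects (SAP 3.1). Assumed 150 per arm under equal allocation, or 180 per active arm under 2:2:1.
- Assumed proportion of eyes abnormal at baseline, b: 5%, 10%, 20%, 30%, the same in both arms.
- Assumed clearance by Visit 5, c: 30% in both arms.
- Assumed new findings in baseline-normal eyes, i: 8% in the worse arm, 2% in the other.

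**Formulas**
- Proportion abnormal at Visit 5 = b(1 − c) + (1 − b)i.
- With equal b and c, the arm difference = (1 − b)(8% − 2%). Clearance cancels, and the true 6.0 points shrink by the factor (1 − b).
- Example at b = 10%: worse arm 0.10 × 0.70 + 0.90 × 0.08 = 0.142; other arm 0.10 × 0.70 + 0.90 × 0.02 = 0.088; difference 0.054.
- Chance of no excess = probability that the worse arm's count is no larger than the other arm's (ties included), treating both counts as binomial. For new findings the binomial proportion is (1 − b)i.

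| Baseline abnormal | Visit 5, worse v other arm | Difference (points) | No excess in Visit 5 count, 150 / 180 per arm | No excess in count of new findings, 150 / 180 per arm |
|---|---|---|---|---|
| 5% | 11.1% v 5.4% | 5.7 | 4% / 3% | 1% / 1% |
| 10% | 14.2% v 8.8% | 5.4 | 8% / 6% | 1% / 1% |
| 20% | 20.4% v 15.6% | 4.8 | 16% / 13% | 2% / 1% |
| 30% | 26.6% v 22.4% | 4.2 | 22% / 19% | 3% / 2% |

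If new findings are compared as rates among baseline-normal eyes rather than as counts, the last column at 150 per arm is about 1% to 2%.

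The expected difference shrinks only modestly. Most of the loss is noise: persisting baseline abnormalities add variation to both counts and carry no information about what happened after dosing.

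**Size of clearance imbalance needed for the expected difference to reach zero:** (1 − b) × 0.06 / b. This is 1.14 at b = 5% (impossible), 0.54 at 10%, 0.24 at 20% and 0.14 at 30%.

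**The case against.** **A reader might infer that the arm difference can disappear.** Counts can be built that way. With 15 abnormal eyes per arm at baseline, 10 new and 10 cleared on Test, and 2 new and 2 cleared on Reference, Visit 5 shows 15 v 15. But clearance then has to track new onset arm by arm. Randomisation balances baseline prevalence and clearance on average, so the expected result is dilution. Complete loss needs chance imbalance or the large clearance differences shown above. The by-visit comparison is valid; it is less sensitive. The table also prints Visit 1, so a baseline imbalance would be visible, though subtracting it still gives only new minus cleared.

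**High baseline corneal abnormality is not supported.** Exclusion criteria 4 and 8 (Protocol 4.3) remove clinically significant ocular disease, including corneal epithelial defects and edema, and corneal abnormalities that would spoil pressure readings in the operative eye. Non-significant findings can remain, but nothing in the documents supports 20% or 30% for the cornea.

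**A reader might infer that a finding seen only at an unscheduled visit is counted nowhere.** That holds for the examination tables only. Protocol 13.1 makes a diagnostic abnormality an adverse event if, among other things, the investigator considers it clinically significant, and a worsening of an existing event is treatment-emergent. SAP 7.8.1 tabulates these by arm. An unscheduled visit that ends participation receives all Visit 5 procedures (Protocol 8.6). What stays uncovered is mainly a new or worsened finding not reported as an event, such as a move from normal to abnormal but not clinically significant.

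**Listings and shells.** Subject listings hold the data but do not aggregate them. The table shells are a separate document (SAP section 9) that was not available, so a shift table there cannot be ruled out. The SAP text does not specify one.

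The physical examination precedent is fair, but that examination is not a named endpoint.

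**Conclusion.** The point holds as a cheap reporting improvement. For two named safety endpoints, no aggregated examination table in the SAP text identifies new or worsened abnormalities by arm. Under the assumed rates, an expected 6.0-point difference is diluted to between 5.7 and 4.2 points. At 150 per arm, the chance of seeing no excess in the worse arm at Visit 5 is about 4% to 22%, against 1% to 3% for a count of new findings; at 180 per arm the chances are somewhat lower. For the cornea, the exclusion criteria point towards the lower end of the prevalence range. Every rate is an assumption, and the arm sizes depend on a redacted ratio. The documents do not support saying that the signal is erased or that the planned comparison is invalid. The primary analyses are unaffected.

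**What to change.** On the safety population, add to SAP 7.8.6 and 7.8.8, per structure, eye and treatment group:

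- (a) A shift table from baseline category to each scheduled post-operative visit at which the examination is done, as 7.8.2 already does to Visit 5 for laboratory tests. For the optic nerve head this has two levels.
- (b) The number and percentage of subjects whose category worsened from baseline at any post-operative examination, including unscheduled and early-discontinuation examinations. For the slit lamp in the study eye, show this with and without Day 1, when surgical changes are likely to dominate.

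Leave the study-eye lens out of (b), or footnote it, because surgery removes it. Keep the by-visit counts. All of this is descriptive, with no tests.

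Cost: SAP wording, a few more tables and some footnotes, from data already collected. No new assessments, subjects or protocol amendment are needed.
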